### **COST EFFECTIVENESS AND UTILITY**

The direct and indirect costs related to gout and its management during the two year study period will be estimated in the nurse led intervention group by recording of the following data:

number of nurse appointments and telephone contacts; duration of each contact; cost of drugs and blood tests; days off work because of acute attacks; any additional health care utilisation during acute attacks. Identical data will be obtained in the standard care group apart from the duration of each GP contact related specifically to gout management – a mean value will be estimated.

Cost utility will be estimated in each group utilising the direct and indirect costs and the SF6D (derived from the SF36). Quality of life during acute attacks will also be obtained in both groups (SF36) and this will be utilised in the cost utility estimations.

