The nurse will follow up the patient at variable time intervals as appropriate to the needs of the patient. It is envisaged that visits will be most frequent (e.g. monthly) in the first 6 months when ULT is being initiated and titrated upwards; subsequently visits may reduce to 3, 6 or 9 monthly depending on difficulty of gout management. Telephone contact to review blood test results and to agree any required action can substitute for visits, and home visits for blood tests and advice are permitted if more convenient (e.g. elderly patients). If home visits are undertaken this will be done in accordance with the University of Nottingham fieldwork guidelines. If the nurse requires any advice concerning treatment strategy (e.g. in patients with serious or multiple co-morbidity, taking multiple drug treatments, or experiencing side-effects) this will be offered by Academic Rheumatology ([name] or, in his absence, another designated Rheumatologist – [name], [name] or [name]). All contacts with the patient (practice visit, home visit, telephone call) and for doctor advice will be logged (date, duration) for subsequent cost effectiveness analysis. Participants will be given a diary to keep during the 2 year study period in which they will record the date and duration of acute attacks of gout.

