### **STATISTICS**

### Methods

The trial statistician ([name]) will oversee the data management, evaluation and analyses. The database will be developed in collaboration with the CTU using access and analysed using SPSS. SUA will be analysed at baseline, 12 months and 24 months. Comparison will be undertaken between the nurse led intervention and control at each observational point. There will be no interim analyses for efficacy or safety. Intention to

Page **19** of **29** Final version 8 –18 May 2015

treat (ITT) analysis will be undertaken to compare treatment effects between groups. Multilevel models will be used for any missing outcome measures. Chi-square test will be used for dichotomous or categorical data and ANOVA test will be used for continuous variables. Adjustment will be made for baseline co-variables as appropriate. Cost per QALY will be estimated from the SF6D and the direct and indirect costs related to gout and its management.

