# 2. Secondary outcomes

- Number of acute attacks in preceding year, year 1 and year 2 within each group and between groups
- Number of patients with tophi at baseline, 12 months and 24 months with each group and between groups
- Mean QoL scores (overall, different domain scores of SF36 and the Gout
   Asssessment Questionnaire (GAQ) including the Gout Impact Scale (GIS) of the GAQ.
   at 0, 12 and 24 months within each group and between groups
- Mean change of QoL scores from baseline to 12 months and 24 months within each group and between groups

**Covariates and baseline predictors:** age, gender, body mass index, disease duration, tophi, associated comorbidity etc.

Task allocation and timetable: The Nottingham CTU will undertake randomisation, development of the database for RCT and the web-based data entry platform. CTU will also conduct data monitoring and quality control for the RCT data. Academic Rheumatology will recruit patients, enter the data through a web-based data entry platform for the RCT data and develop an independent database for the observational group. Both datasets are not open for any interim analysis between baseline and 24 months to keep the randomisation. Analysis will start after 24 months when the data has been fully completed, quality checked over and closed. Analysis for clinical effectiveness (efficacy and side effects) will be completed in 3 months after the closing date of the data. Analysis for cost-effectiveness will be completed in 12 months, as it requires acquisition of additional data for cost. In brief:

- Recruitment 8 months
- RCT and observation 24 months
- Results for clinical effectiveness 3 months
- Results for cost-effectiveness 12 months

Economic Analyses Plan.

Two economic analyses are planned: the first being an economic analysis alongside the RCT and the second modelling the costs and benefits over a longer time horizon. The base case in both models would use an NHS perspective, with a societal perspective (that include indirect costs such as lost productivity) being undertaken in a sensitivity analysis.

Economic analysis alongside the RCT

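### Work time lost to attending gout care is neither collected nor valued in either arm, so analyses that include indirect costs probably, though not certainly, lean towards nurse-led care

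*Supplement*

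**What the plan says.** The Cost effectiveness and utility section of protocol version 8 lists the cost data for the nurse-led arm. On resources it names "number of nurse appointments and telephone contacts; duration of each contact; cost of drugs and blood tests". On productivity it names only "days off work because of acute attacks", and the list ends with further use of health care during attacks. For controls it adds: "Identical data will be obtained in the standard care group apart from the duration of each GP contact related specifically to gout management", for which a mean value is to be used.

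Indirect costs then enter the result. The same section says "Cost utility will be estimated in each group utilising the direct and indirect costs and the SF6D (derived from the SF36"), and Statistics, Methods says "Cost per QALY will be estimated from the SF6D and the direct and indirect costs related to gout and its management". Neither names a perspective.

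The Economic Analyses Plan (analysis plan of 17 July 2013) does name one. In both planned economic analyses the base case takes the NHS perspective, and "a societal perspective (that include indirect costs such as lost productivity") is left to a sensitivity analysis. Its part on the analysis alongside the RCT adds that costs cover the interventions and what follows from them, and that indirect as well as direct NHS costs are recorded.

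On contacts, the Nurse intervention section expects that "visits will be most frequent (e.g. monthly) in the first 6 months", and then every 3, 6 or 9 months. Telephone calls may replace visits, home visits are allowed, and each contact is logged with date and duration for the economic analysis. The Control/Standard Care arm section gives controls one nurse consultation, blood samples at 12 and 24 months, and continuing GP care. The study regimen table has a record of GP visits for gout, marked for the control arm only.

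**The concern.** The one productivity item measures absence that the intervention is meant to reduce. Time away from work in order to receive care has no item. A comparison that includes productivity therefore takes credit for attacks avoided without charging for the attendance that helped to avoid them. If one arm attends more often, the gap does not cancel between arms.

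Cost effectiveness is part of the primary objective. A societal result built on this list would be incomplete by construction, and the analysis plan's statement that indirect costs of the interventions are recorded would lack the data to support it.

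**Working it through.** The documents give no hours per attendance, employment share, wage or cost per QALY, so there is no figure of the plan's own to reproduce. The check has three steps.

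**1. Which time is covered**

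| Source of lost work time | Listed as a productivity item? | Related record |
|---|---|---|
| Acute attacks | Yes, both arms | Days off work |
| Nurse contacts | No | Nurse arm: number, date and duration logged |
| GP visits for gout | No | Record of visits, control arm |
| Blood tests at 12 and 24 months | No | Scheduled in both arms |

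The omission is in both arms. Logged contact duration captures part of the nurse-arm time, but not travel or actual absence.

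**2. Nurse-arm contacts implied by the follow-up pattern**

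Monthly contact for 6 months, then one every *g* months for the remaining 18, gives n = 6 + 18/g:

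- g = 3: 6 + 6 = 12
- g = 6: 6 + 3 = 9
- g = 9: 6 + 2 = 8

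**3. Illustration of size**

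Assumptions, none from the documents: share of contacts in person and in working hours s = 0.5 to 1; share employed e = 0.3 to 0.6; hours lost per contact h = 1 to 4; working day 7.5 hours.

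Unrecorded days per nurse-arm participant = n × s × e × h / 7.5.

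| n | Lowest | Highest |
|---|---|---|
| 12 | 12 × 0.5 × 0.3 × 1 / 7.5 = 0.24 | 12 × 1 × 0.6 × 4 / 7.5 = 3.84 |
| 9 | 9 × 0.5 × 0.3 × 1 / 7.5 = 0.18 | 9 × 1 × 0.6 × 4 / 7.5 = 2.88 |
| 8 | 8 × 0.5 × 0.3 × 1 / 7.5 = 0.16 | 8 × 1 × 0.6 × 4 / 7.5 = 2.56 |

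These figures are gross. The bias is the difference between arms, so control attendances *k* must be subtracted. With h = 2, e = 0.5 and every attendance in working hours, net days = (n − k) × 2 × 0.5 / 7.5:

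| k | n = 12 | n = 8 |
|---|---|---|
| 0 | 1.60 | 1.07 |
| 4 | 1.07 | 0.53 |
| 8 | 0.53 | 0 |
| 12 | 0 | −0.53 |

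At equal hours per attendance and equal employment in the two arms, the omission is neutral when k = n × s. That is between 8 × 0.5 = 4 and 12 × 1 = 12 control attendances over two years. Below that point it favours nurse-led care; above it, standard care.

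**The case against.** A reader might infer more than the documents support, in four ways.

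- *That the plan values attendance time at zero.* No rule says so. The analysis plan states an intention to record indirect costs of the interventions, and the nurse contacts are logged for economic use. What is missing is an item and a method of valuing it.
- *That the omission is one-sided and always helps nurse-led care.* The same list applies to controls, whose comparator is GP care and not merely one nurse consultation. Their GP and blood-test time is uncounted too. Telephone and home contacts reduce the nurse-arm time. The direction stays likely, because the protocol's background describes usual care as giving urate-lowering therapy to about one third of patients, usually at a fixed dose and without monitoring, which does not suggest frequent GP attendance for gout. It is not certain.
- *That the main cost per QALY is biased.* Under the analysis plan the base case takes the NHS perspective, so lost productivity does not enter it. Version 8 can be read otherwise, since it puts indirect costs into the cost per QALY and names no perspective. Its wording on this is unchanged from version 4 of February 2013, however, and the analysis plan was written after that and is more specific. The two texts need reconciling; they do not show that the base case is affected.
- *That the omitted time matches the absence from a prevented attack.* The documents give neither days off per attack nor hours per visit. Any such comparison sets one assumption against another. There is also no upper age limit, so the employed share may be low.

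These objections limit the size and reach of the point. They do not supply the missing item: as written, no analysis that includes indirect costs can count attendance time from the listed data without a further assumption.

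**Conclusion.** The point holds in a limited form. Work time lost to attending gout care is neither collected nor valued in either arm, which does not fit the analysis plan's statement on recording indirect costs. Because the nurse arm is expected to have about 8 to 12 contacts, the net omission probably favours nurse-led care. It does so wherever indirect costs are included: the societal sensitivity analysis in both economic analyses, and the cost per QALY as version 8 words it. The NHS-perspective base case is not touched.

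The size cannot be determined from the documents. The illustration gives about 0.2 to 3.8 days per nurse-arm participant before control attendances are subtracted, and the net figure can be zero or reverse if controls attend often. It rests wholly on the assumed employment share, in-person share and hours per contact.

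**What to change.** If data are still being collected, widen the productivity item in Cost effectiveness and utility to time off work because of gout, covering attacks and attendance for nurse, GP or blood-test appointments. Ask it identically in both arms, for example in the 12- and 24-month questionnaires.

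If collection is complete, apply a stated time per in-person attendance, with a range, to the logged nurse contacts and the recorded GP visits. Do this in both arms and in every analysis that includes indirect costs. The regimen table marks the GP-visit record for controls only, so say how GP visits for gout in the nurse arm are counted.

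In either case, state in Statistics, Methods and in Cost effectiveness and utility which perspective the cost per QALY takes, and bring those sections into line with the Economic Analyses Plan.

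The cost is a slightly longer form or one added assumption, a little analysis work, and possibly a less favourable societal result for nurse-led care.

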### **ETHICAL AND REGULATORY ASPECTS**

### **Involvement of General Practitioner**

**Nurse led group (RCT):** GPs will be informed if their patients are randomised to the nurse led group and will be kept informed with respect to changes to their patients' gout medications. If the nurse detects any adverse event or comorbidity unrelated to gout and its management the GP will also be directly informed.

**Standard care group (RCT):** We will not inform the GP that their patient has been randomised to the ongoing standard care group since this may 'contaminate' the GP care

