### MONITORING STUDY PARTICIPANTS SUITABILITY TO CONTINUE IN THE STUDY

Prior to contacting participants in the RCT standard care arm, at one and two years, the GP surgeries will be provided with a list of participants in these groups and asked to check their records to ensure that patients are still registered with surgery, living at the same address and are suitable to be contacted. If this is not feasible, the Health and Social Care Information Centre or other central UK NHS body will be contacted to confirm the contact address and health status of patients participating in the trial. As regular contact will be maintained with participants in the RCT Nurse Intervention arm it is envisaged that participants/family members will keep the study team informed. If there is any reason to believe that an individual status may have changed, e.g. no reply to correspondence, telephone calls or non-attendance for appointments the GP surgery will again be contacted.

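### Standard-care allocation is withheld from GPs to prevent contamination, but the list sent to surgeries at one and two years can reveal it, with a year of GP care left before the primary endpoint

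*Supplement*

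**What the plan says.** All references are to protocol version 8 (18 May 2015) unless stated.

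- **Ethical and Regulatory Aspects, Involvement of General Practitioner.** For the standard-care group: "We will not inform the GP that their patient has been randomised to the ongoing standard care group", and the reason is "since this may 'contaminate' the GP care". The same section says that GPs are told when a patient is allocated to the nurse arm and are kept informed of changes to that patient's gout drugs.
- **Monitoring Study Participants Suitability to Continue in the Study.** The procedure begins "Prior to contacting participants in the RCT standard care arm" and continues "at one and two years, the GP surgeries will be provided with a list of participants in these groups". Surgeries are "asked to check their records to ensure that patients are still registered with surgery", and also that the address is unchanged and that contact is appropriate. The alternative route comes second: "If this is not feasible, the Health and Social Care Information Centre or other central UK NHS body will be contacted". It is said to cover address and health status. The nurse arm has no routine list. Its surgeries are approached only when there is reason to think a participant's status has changed.
- **Control/Standard Care arm.** The comparator is the GP's own care.
- **Primary endpoint and Secondary endpoints.** The primary endpoint is the percentage at the urate target at the end of year 2. Attacks are assessed in the second year, and quality of life at the end of the study.

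**The concern.** Patients are randomised individually within practices, so the same GPs may have patients in both arms. The protocol itself judges that a GP who knows a patient is a control may treat that patient differently, and it withholds the information for that reason. The list procedure can then supply that information.

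If a list prompts a GP to review gout care, controls drift towards the care that the nurse arm receives, and the comparison shrinks towards no difference. The exposed period after the first list is year 2. That is the year in which attacks are assessed, and it ends with the primary urate measurement and the final quality-of-life scores. Costs and QALYs would be affected in the same way.

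**Working it through.** The core of the point is a comparison of text. The plan gives no contamination figure to reproduce.

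**Step 1. Does the list identify controls?** The procedure is introduced for the standard-care arm only, and the nurse arm gets no routine list. GPs already know their nurse-arm patients. So even with no arm label, a listed trial patient who is not known to be in the nurse arm can be taken to be a control. The section does not mask the list or keep it from the treating GP. Listing both arms together would not help, because controls could still be found by elimination.

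**Step 2. Is there time for it to act?** First list at about 12 months, primary endpoint at 24 months: 24 − 12 = about 12 months of GP care after disclosure. The second list goes out just before the 24-month assessment and has almost no time to act. Only the 12-month list matters for the endpoints.

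**Step 3. Illustration for the primary endpoint.** The inputs come from Power calculations: 23% of survey patients on urate-lowering therapy (ULT) and 75% of those not on it were above 360 µmol/L. Target rates are therefore taken as 77% and 25%. Analysed per arm: 256 less 10%, about 230. Let c be the share of controls prompted onto treatment. This is an assumption; the documents give no value.

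Control rate = 25% + c × (77% − 25%), so each 10% prompted adds 5.2 points. Power = Φ[(difference − 1.96 × SE under the null) / SE under the alternative], two-sided 5%.

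| c | Control rate | Difference | Power, 230 per arm |
|---|---|---|---|
| 0 | 25% | 52 points | >99% |
| 25% | 38% | 39 points | >99% |
| 50% | 51% | 26 points | >99% |
| 75% | 64% | 13 points | 87% |

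A less favourable start puts 30% of controls on treatment already, as in the survey: 0.30 × 77% + 0.70 × 25% = 40.6%. Closing half of the remaining shortfall then gives 58.8%, a difference of 18.2 points and power of about 99%. Closing three quarters gives 67.9%, 9.1 points and 59%.

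**Step 4. Illustration for attacks.** Survey rates of 57% and 32%, 230 per arm. Closing 10%, 25% or 50% of the gap gives control rates of 54.5%, 50.75% or 44.5%, and power of 99.9%, 98.5% or 79%. The survey rate stands in for the trial's endpoint, which is the percentage with fewer attacks.

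**Step 5. Illustration for quality of life.** Power calculations gives 233 per arm at 80% power; the significance level is read as 5%, as in the Synopsis. The implied standardised effect is (1.960 + 0.842) × √(2/233) = 0.2596. If prompted controls gain the full effect, power at 230 per arm is Φ[0.2596 × (1 − c) × √115 − 1.960]:

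- c = 0: Φ(0.824) = 79.5%
- c = 10%: Φ(0.546) = 70.7%
- c = 20%: Φ(0.267) = 60.5%

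With the survey means and SD used directly (16.41 − 15.67 = 0.74, SD 3.09, 233 per arm), power is 73% at c = 0, 64% at 10% and 49% at 25%.

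**The case against.** The strongest case is that the list is a modest administrative check and a small leak beside others the design accepts.

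- **It is not a clinical review.** It goes to surgeries to confirm registration, address and fitness to be contacted, and asks nothing about gout or drugs. Surgery staff already handle trial mailings, as Recruitment via collaborating GP surgeries shows. This stands, but nothing in the text keeps the list from the treating GP.
- **The list may not be controls only.** The wording refers to groups in the plural, and the analysis plan mentions an observational group. No arm label is described. So the list can reveal controls; the text does not make it certain that it will.
- **Other routes exist from baseline.** Controls know their allocation, and the Synopsis says those who ask about lifestyle or ULT are referred to their GP. This stands as well, but unavoidable leaks are no reason to add one that the trial team creates itself.
- **GPs may not respond.** The background section says education alone rarely changes GP behaviour, and an address check is a weaker prompt. That argues against assuming a large prompted share.
- **There are other protections.** Best-practice strategies are not described to participants before randomisation, and the control visit is confined to acute attacks. A reader might infer that withholding allocation from the GP is the only guard against contamination; the documents do not support that.

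The between-arm comparison at 12 months falls before the first list has had time to act, so it offers a partial reference. It does not protect the 24-month endpoint.

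**Conclusion.** The two sections of the current protocol conflict and must be reconciled. One withholds standard-care allocation from GPs; the other can disclose it a year before the primary endpoint. The direction of any effect is towards no difference.

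The size is unknown. A reader might infer that the control arm will be contaminated, or that the primary comparison is short of power. The documents show only that the disclosure is possible. Power for the primary endpoint stays near or above 99% with half the control shortfall closed, under either starting rate, and weakens only at extreme contamination. What is more exposed is the size of the effect, year-2 attacks, quality of life and cost-effectiveness.

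The quality-of-life figures are illustrations only. They rest on an assumed prompted share and on prompted controls gaining the whole difference seen in a cross-sectional survey within at most 12 months, which is generous to contamination. The case for changing the procedure is that the leak is avoidable and cheap to close, not that a given loss of power has been shown.

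**What to change.** In Monitoring Study Participants Suitability to Continue in the Study, reverse the order of the two routes at both 12 and 24 months:

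1. Check address and health status through the central NHS body first.
2. Contact the surgery only for individuals whose status remains unresolved, through administrative staff and without stating the trial arm.

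Add a cross-reference in Involvement of General Practitioner so that the two sections agree.

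The cost is a small wording change, a change in office procedure and a slightly slower check. It needs no extra participants and no change to design, endpoints or analysis.
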